3.2. Final Analyses

The final planned analyses will be performed after the completion of the following sequential steps:

1. All participants screened for the study prior to its termination will be part of the final analysis.
2. All required database cleaning activities have been completed and final database release (DBR) and database freeze (DBF) has been declared by Data Management.
3. All criteria for unblinding the randomisation codes have been met.
4. Randomisation codes have been distributed according to RandAll NG procedures.

3.3. Changes to the Protocol Defined Statistical Analysis Plan

[Table 2](#) details the changes and deviations to the originally planned statistical analysis specified in the protocol [(Dated: 29-Nov-2017)].

Table 2 Changes to Protocol Defined Statistical Analysis Plan

Protocol	Reporting & Analysis Plan	
Statistical Analysis Plan	Statistical Analysis Plan	Rationale for Changes

 An exploratory statistical analysis may be performed on the biomarker data if deemed appropriate. 	
 Biomarker data will be summarized 	
 Lack of data following study termination

Protocol	Reporting & Analysis Plan	
Statistical Analysis Plan	Statistical Analysis Plan	Rationale for Changes

 PK/PD analysis of the biomarkers will be conducted between PD biomarkers and PK, other exploratory PK/PD analysis of the biomarkers may be conducted should changes in biomarkers be detected 	
 PK/PD analysis will not be conducted 	

4. ANALYSIS POPULATIONS

Population	Definition / Criteria	Analyses Evaluated
Enrolled Population	
 Defined as all subjects who were enrolled for the trial irrespective of whether they were randomized or not and for whom a record exists on the study database. 	
 Study Population
Screened Subjects	
 Screened Subjects population will be defined as all subjects who were screened regardless of whether they were successful 	
 Screen failures
All Subjects	
 All Subjects population will be defined as all subjects randomised to treatment who receive at least one dose of study treatment. Subjects will be reported based on the treatment they actually received 	
 Study Population Safety PD
PK Concentration	
 PK Concentration population will be defined as all subjects for whom a pharmacokinetic sample was obtained and analysed. 	
 PK PK/PD
PK Parameter	
 PK Parameter population will be defined as all subjects in the 'PK Concentration' population who provide pharmacokinetic parameters. 	
 PK

NOTES:

- Please refer to [11.10](#): List of Data Displays which details the population to be used for each display being generated.
- Additional populations (to those described in the protocol) have been created for the purpose of required displays

4.1. Protocol Deviations

Important protocol deviations (including deviations related to study inclusion/exclusion criteria, conduct of the trial, patient management or patient assessment) will be summarised and listed.

Protocol deviations will be tracked by the study team throughout the conduct of the study in accordance with the Protocol Deviation Management Plan version 1 dated: 2nd August 2017.

- Data will be reviewed prior to unblinding and freezing the database to ensure all important deviations and deviations which may lead to exclusion from the analysis are captured and categorised on the protocol deviations dataset.
- This dataset will be the basis for the summaries and listings of protocol deviations.

A separate summary and listing of all inclusion/exclusion criteria deviations will also be provided. This summary will be based on data as recorded on the inclusion/exclusion page of PIMS.

5. CONSIDERATIONS FOR DATA ANALYSES AND DATA HANDLING CONVENTIONS

5.1. Study Treatment & Sub-group Display Descriptors

Treatment Details Descriptions			
RandAll NG		Data Displays for Reporting	
Code	Description	Description ^[1]	Order ^[2]
Part A			
A1	Part A. Cohort 1 GSK3335065 (IV) Active Dose 1	GSK3335065 0.1 mg	2
A2	Part A. Cohort 2 GSK3335065 (IV) Active Dose 2	GSK3335065 0.25 mg	3
AA3	Part A. Cohort 3 GSK3335065 (IV) Active Dose 3	GSK3335065 1.3 mg	4
AA4	Part A. Cohort 4 GSK3335065 (IV) Active Dose 4	GSK3335065 Dose 4	5
AA5	Part A. Cohort 5 GSK3335065 (IV) Active Dose 5	GSK3335065 Dose 5	6
AA6	Part A. Cohort 6 GSK3335065 (IV) Active Dose 6	GSK3335065 Dose 6	7
AA7	Part A. Cohort 7 GSK3335065 (IV) Active Dose 7	GSK3335065 Dose 7	8
AA8	Part A. Cohort 8 GSK3335065 (IV) Active Dose 8	GSK3335065 Dose 8	9
PA1/ PA2/ PA3/ PA4/ PA5/ PA6/ PA7/ PA8 ^[3]	Part A. Placebo Cohort 1/ Part A. Placebo Cohort 2/ Part A. Placebo Cohort 3/ Part A. Placebo Cohort 4/ Part A. Placebo Cohort 5/ Part A. Placebo Cohort 6/ Part A. Placebo Cohort 7/ Part A. Placebo Cohort 8	Placebo	1
Part B			
B9	Part B. Cohort 9 GSK3335065 (IV) Active Dose 9	GSK3335065 Dose 9	2
B10	Part B. Cohort 10 GSK3335065 (IV) Active Dose 10	GSK3335065 Dose 10	3

Treatment Details Descriptions			
RandAll NG		Data Displays for Reporting	
Code	Description	Description ^[1]	Order ^[2]
B11	Part B. Cohort 11 GSK3335065 (IV) Active Dose 11	GSK3335065 Dose 11	4
B12	Part B. Cohort 12 GSK3335065 (IV) Active Dose 12	GSK3335065 Dose 12	5
PB9/ PB10/ PB11/ PB12	Part B. Placebo Cohort 9 / Part B. Placebo Cohort 10/ Part B. Placebo Cohort 11/ Part B. Placebo Cohort 12	Placebo	1
Part C			
C13	Part C. Cohort 13 GSK3335065 (IV) Active Dose 13	GSK3335065 Dose 13	2
C14	Part C. Cohort 14 GSK3335065 (IV) Active Dose 14	GSK3335065 Dose 14	3
PC13/ PC14	Part C. Placebo Cohort 13/ Part C. Placebo Cohort 14	Placebo	1

NOTES:

[1] As the study was terminated during Part A Cohort 3 the remaining doses are not completed

[2] Order represents treatments being presented in TFL, as appropriate.

[3] Placebo is pooled by part for all analysis except the pharmacodynamic analysis

Treatment comparisons will be displayed as follows using the descriptors as specified:

1. GSK3335065 X.X mg vs Placebo
2. GSK3335065 Y.Y mg vs Placebo etc.

5.2. Baseline Definitions

For all endpoints apart from the PD biomarkers, the baseline value will be the latest pre-dose assessment. For the PD data, the baseline will be the average of all pre-dose measurements (incl. Day -1). Unless otherwise stated in the schedule of activities, the mean of replicate assessments at any given time point will be used as the value for that time point (e.g. for ECGs).

Unless otherwise stated, if baseline data is missing no derivation will be performed and baseline will be set to missing.

5.2.1. Derivations and Handling of Missing Baseline Data

Definition	Reporting Details
Change from Baseline	= Post-Dose Visit Value – Baseline
% Change from Baseline	= $100 \times [(Post-Dose Visit Value - Baseline) / Baseline]$
Maximum Change from Baseline	= Calculate the change from baseline at each given timepoint and determine the maximum change

NOTES :

- Unless otherwise specified, the baseline definitions specified in Section 5.2 Baseline Definitions will be used for derivations for endpoints / parameters and indicated on summaries and listings.
- Unless otherwise stated, if baseline data is missing no derivation will be performed and will be set to missing.
- The baseline definition will be footnoted on all change from baseline displays.

5.3. Other Considerations for Data Analyses and Data Handling Conventions

Other considerations for data analyses and data handling conventions are outlined in the appendices:

Section	Component
11.3	Appendix 3: Assessment Windows
11.4	Appendix 4: Study Phases and Treatment Emergent Adverse Events
11.5	Appendix 5: Data Display Standards & Handling Conventions
11.6	Appendix 6: Derived and Transformed Data
11.7	Appendix 7: Reporting Standards for Missing Data
11.8	Appendix 8: Values of Potential Clinical Importance

6. STUDY POPULATION ANALYSES

6.1. Overview of Planned Study Population Analyses

The study population analyses will be based on the “Screened”, “Enrolled” and “All Subjects” population, unless otherwise specified.

Study population analyses including analyses of subject’s disposition, protocol deviations, demographic and baseline characteristics, prior and concomitant medications, and exposure and treatment compliance will be based on GSK Core Data Standards. Details of the planned displays are presented in [Appendix 10: List of Data Displays](#) and [Table 3](#) provides an overview of the analysis required during interim and final reporting.

Table 3 Overview of Planned Study Population Analyses

Endpoint / Parameter / Display Type	Data Displays Generated		
	Table	Figure	Listing
Subject Disposition			
Subject Status and Reason for Study Withdrawal	Y		
Reasons for Subject Withdrawal			Y
Screening Status and Reasons for Screen Failure	Y		Y
Subjects for Whom the Treatment Blind was Broken			Y
Randomized and Actual Treatments			Y
Protocol Deviations			
Important Protocol Deviations	Y		Y
Subjects with Inclusion/Exclusion Criteria Deviations			Y
Populations Analysed			
Study Populations	Y		
Participants Excluded from any population			Y
Demographic and Baseline Characteristics			
Demographic Characteristics	Y		Y
Age Ranges	Y		
Race and Racial Combinations	Y		Y [1]
Prior and Concomitant Medications			
Current Medical Conditions	Y		
Past Medical Conditions	Y		
Concomitant Medications	Y		Y
Exposure and Treatment Compliance			
Exposure to Study Treatment	Y		Y

NOTES:

- Y = Yes display generated at end of study only

[1] Listing of race.

7. SAFETY ANALYSES

The safety analyses will be based on the “All Subjects” population, unless otherwise specified.

7.1. Adverse Events Analyses

Adverse events analyses including the analysis of adverse events (AEs), Serious (SAEs) and other significant AEs will be based on GSK Core Data Standards. The details of the planned displays are provided in [Appendix 10: List of Data Displays](#). [Table 4](#) provides an overview of the planned analyses.

Table 4 Overview of Planned Adverse Event Analyses

Endpoint / Parameter/ Display Type	Absolute		
	Summary		Individual
	T	F	L
Adverse Events (AEs)			
All AEs by Maximum Intensity and SOC and PT	Y		Y
Common AEs (2 or more subjects) by Overall Frequency	Y		
Common Non-serious AEs (2 or more subjects) by SOC and PT (Number of Participants and Occurrences)	Y		
Drug-Related AEs by SOC and PT and Maximum Intensity	Y		
Subject Numbers for Individual AEs			Y
Relationship Between AE SOCs, PT and Verbatim Text			Y
Assessment at Infusion site			Y
Serious and Other Significant AEs			
All SAEs	Y		Y
All SAEs by SOC and PT (Number of Participants and Occurrences)	Y		
Fatal Serious AEs			Y
Drug-Related Serious AEs	Y		
Drug-Related Fatal Serious AEs			Y
Reasons for Considering as a Serious AE			Y
AEs Leading to Withdrawal from Study / Permanent Discontinuation of Study Treatment by SOC and PT	Y		Y

7.2. Clinical Laboratory Analyses

Laboratory evaluations including the analyses of Chemistry laboratory tests, Hematology laboratory tests, Urinalysis, and liver function tests will be based on GSK Core Data Standards. The details of the planned displays are in [Appendix 10: List of Data Displays](#).

Table 5 Overview of Planned Clinical Laboratory Analyses

Endpoint / Parameter/ Display Type	Absolute			Change from BL		
	Summary		Individual	Summary		Individual
	T	F	L	T	F	L
Chemistry						
Chemistry Changes from Baseline				Y		
Worst Case Chemistry Results Relative to Normal Range Post-Baseline Relative to Baseline	Y					
Chemistry Results by PCI	Y					
Hematology						
Hematology Changes From Baseline				Y		
Worst Case Hematology Results Relative to Normal Range Post-Baseline Relative to Baseline	Y					
Hematology Results by PCI	Y					
Urinalysis						
Urine Concentration Changes from Baseline				Y		
Worst Case Urinalysis Results Relative to Normal Range Post-Baseline Relative to Baseline	Y					
Urinalysis Results by PCI	Y					
Hepatobiliary (Liver)						
Liver Monitoring/Stopping Event Reporting	Y					
Hepatobiliary Laboratory Abnormalities	Y					
All Laboratory						
All Laboratory Data for Subjects with any Value of PCI			Y			
Laboratory Values of PCI			Y			
Laboratory Data with Character Results ^[1]			Y			
Urinalysis Data for Participants with Any Value of PCI			Y			

NOTES:

- T = Table, F = Figures, L = Listings, Y = Yes display generated at end of study only, YI = Yes display generated at end of study and at interim, PCI = Potential Clinical Importance
- Summary = Represents TFL related to any summaries (i.e. descriptive statistics) of the observed raw data.
- Individual = Represents FL related to any displays of individual subject observed raw data.
- ^[1] Urine dipstick results

7.3. Other Safety Analyses

The analyses of non-laboratory safety test results including ECGs and vital signs will be based on GSK Core Data Standards, unless otherwise specified. The details of the planned displays are presented in [Appendix 10: List of Data Displays](#).

Table 6 Overview of Planned Other Safety Analyses

Endpoint / Parameter/ Display Type	Absolute			Change from BL		
	Summary		Individual	Summary		Individual
	T	F	L	T	F	L
ECG						
ECG Findings	Y					
Maximum QTc Values Post-Baseline Relative to Baseline by Category	Y					
ECG Values by Visit [1]	Y		Y	Y		Y
Summary of Maximum Increase in QTc Values Post-Baseline Relative to Baseline by Category	Y					
All ECG Values for Subjects with any Value of PCI			Y			
ECG Values of PCI			Y			
All ECG Findings for Participants with an Abnormal ECG Finding			Y			
Abnormal ECG Findings			Y			
Echocardiogram and Continuous ECG monitoring						
Echocardiogram Findings			Y			
ECG monitoring and Telemetry Findings			Y			
Vital Signs						
Vital Signs by Visit	Y		Y	Y		Y
Worst Case Vital Signs Results Relative to Normal Range Post-Baseline Relative to Baseline	Y					
All Vital Signs for Subjects with any Value of PCI			Y			Y
Vital Signs of PCI			Y	Y		Y

NOTES:

- T = Table, F = Figures, L = Listings, Y = Yes display generated at the end of the study, PCI = Potential Clinical Importance
- Summary = Represents TFL related to any summaries (i.e. descriptive statistics) of the observed raw data.
- Individual = Represents FL related to any displays of individual subject observed raw data.

[1] Includes continuous cardiac monitoring results

8. PHARMACOKINETIC ANALYSES

8.1. Primary Pharmacokinetic Analyses

8.1.1. Endpoint / Variables

The pharmacokinetic (PK) parameters of interest are: $AUC_{(0-t)}$, $AUC_{(0-\infty)}$, t_{last} , C_{max} , C_{avg} , t_{max} , CL , V , and $t_{1/2}$.

8.1.1.1. Drug Concentration Measures

Refer to [Appendix 5](#): Data Display Standards & Handling Conventions (Section 11.5.3 Reporting Standards for Pharmacokinetic)

8.1.1.2. Derived Pharmacokinetic Parameters

The analysis will be performed by, or be under the direct auspices of, Clinical Pharmacology Modelling and Simulation (CPMS), GlaxoSmithKline. PK parameters will be calculated by standard non-compartmental analysis in WinNonLin, using concentration-time data based on actual sample times, as described in the standard operating procedure SOP-314000. All derived PK parameters will be listed and summarized according to SOP-BMD-4002 (Standard Statistical Methods for the analysis of Pharmacokinetic Data).

Table 7 Derived Pharmacokinetic Parameters

Parameter	Parameter Description
AUC(0-t)	Area under the concentration-time curve from time zero to the time of the last quantifiable concentration ($C(t)$) will be calculated using the linear trapezoidal rule for each incremental trapezoid and the log trapezoidal rule for each decremental trapezoid.
AUC($0-\infty$)	Area under the concentration-time curve extrapolated to infinity will be calculated as: $AUC = AUC(0-t) + C(t) / \lambda_z$
%AUCex	The percentage of AUC ($0-\infty$) obtained by extrapolation (%AUCex) will be calculated as: $[\frac{AUC(0-\infty)}{AUC(0-t)} - 1] \times 100$
Cmax	Maximum observed concentration, determined directly from the concentration-time data.
tmax	Time to reach Cmax, determined directly from the concentration-time data.
t $_{1/2}$	Apparent terminal half-life will be calculated as: $t_{1/2} = \ln 2 / \lambda_z$
Clearance (CL)	$CL = Dose / AUC (0-\infty)$
Volume of Distribution at Steady State (Vdss)	$Vdss = CL \times MRT_{iv}$ where MRT _{iv} is Mean Residence Time and Mean Absorption Time and is given by $MRT_{iv} = (AUMC(0-\infty)/AUC(0-\infty)) - T/2$ where T is the infusion duration

Parameter	Parameter Description
tlast	Time of the last measurable concentration, determined directly from the concentration-time data.

NOTES:

- Additional parameters may be included as required.
- Lambda_z is the terminal phase rate constant.

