9.3. Treatment of Overdose

For this study, any dose of GSK3335065 greater than the agreed dose for a particular cohort, dosing session or study part will be considered as an overdose.

GSK does not recommend specific treatment for an overdose

In the event of an overdose the investigator or treating physician should:

1. Contact the Medical Monitor immediately
2. Closely monitor the subject for adverse events (AEs)/serious adverse events (SAEs) and laboratory abnormalities until GSK3335065 can no longer be detected systemically (at least 8 days which is equivalent to 5 times the observed preliminary half life of ~35 hours for GSK3335065).
3. Obtain a plasma sample for pharmacokinetic (PK) analysis within 1 days from the date of the last dose of study treatment if requested by the Medical Monitor (determined on a case-by-case basis)

4. Document the quantity of the excess dose as well as the duration of the overdosing in the CRF.

Decisions regarding dose interruptions or modifications will be made by the investigator in consultation with the Medical Monitor based on the clinical evaluation of the subject.

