Reporting of Pharmacokinetic Parameters	
Descriptive Summary Statistics (Log Transformed)	N, n, geometric mean, 95% CI of geometric mean, standard deviation (SD) of logged data and [between and or within] geometric coefficient of variation (CV _{b/w} (%)) will be reported. [1] CV _b (%) = $\sqrt{(\exp(SD^2) - 1) * 100}$ (SD = SD of log transformed data) (MSE = mean square error from mixed effect model of loge-transformed data).
Parameters Not Being Log Transformed	T _{max} , t _{1/2} , t _{last}
Summary Tables	C _{max} , t _{max} , AUC(0-t), AUC (0-∞), CL, V, t _{1/2} , and t _{last} as data permit
Listings	All parameters collected in the dataset will be listed
Graphical Displays	

 Refer to IDSL Statistical Principals 7.01 to 7.13. 	

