11.5.3. Reporting Standards for Pharmacokinetic

Pharmacokinetic Concentration Data	
PC Windows Non-Linear (WNL) File	PC WNL file (CSV format) for the non-compartmental analysis by Clinical Pharmacology Modelling and Simulation function will be created according to the [PKOne standards] Note: Concentration values will be imputed as per GUI_51487
Descriptive Summary Statistics, Graphical Displays and Listings	Refer to IDSL PK Display Standards. Refer to IDSL Statistical Principle 6.06.1. Note: Concentration values will be imputed as per GUI_51487 for descriptive summary statistics/analysis and summarized graphical displays only.
NONMEM/Pop PK File	Not applicable.
NONMEM/PK/PD File	Not applicable.
Pharmacokinetic Parameter Derivation	
PK Parameter to be Derived by Programmer	Not applicable.
Pharmacokinetic Parameter Data	
Is NQ impacted PK Parameters Rule Being Followed	Yes, refer to SOP_3140000
Descriptive Summary Statistics, Graphical Displays and Listings	Refer to IDSL PK Display Standards.

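### SAP Table 7 defines %AUCex as a share of AUC(0-∞), but its formula divides by AUC(0-t), so the extrapolated share is overstated if the formula is followed

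*SAP*

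**What the plan says.** Three rows of Table 7 in SAP Section 8.1.1.2 matter here.

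- AUC(0-t) is the "Area under the concentration-time curve from time zero to the time of the last quantifiable concentration", that is, the observed area.
- AUC(0-∞) is the "Area under the concentration-time curve extrapolated to infinity will be calculated as" AUC(0-t) + C(t)/λz. The extrapolated area is therefore C(t)/λz.
- %AUCex is worded as the percentage of AUC(0-∞) "obtained by extrapolation (%AUCex) will be calculated as" followed by [AUC(0-∞)/AUC(0-t) − 1] × 100.

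On reporting, the same section states: "All derived PK parameters will be listed and summarized according to SOP-BMD-4002". SAP Section 11.5.2 adds, for listings: "All parameters collected in the dataset will be listed". However, the list in Section 8.1.1 that begins "The pharmacokinetic (PK) parameters of interest are" does not include %AUCex, and neither does the summary-table list in Section 11.5.2.

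No other part of the SAP or protocol defines %AUCex or sets a limit on it.

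**The concern.** The words and the formula in the %AUCex row use different denominators, so they define different quantities. The wording gives extrapolated area over total area. The formula gives extrapolated area over observed area. They agree only when nothing is extrapolated.

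%AUCex tells a reader how far AUC(0-∞), and clearance computed as dose over AUC(0-∞), rest on the fitted terminal slope rather than on measured concentrations. Overstating it makes those estimates look less well supported than they are.

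This could matter mainly in Cohorts 1 and 2, which supply nearly all the PK data. Each planned 6 active participants (Protocol Section 10.2.1), with sampling to 72 h (Protocol Section 9.5.1). The half-life turned out well above the predicted 7.8 h (Protocol Section 5.4.1), and Protocol Section 9.3 relies on "5 times the observed preliminary half life of ~35 hours for GSK3335065". Cohort 3 stopped after sentinel dosing (SAP Section 1), with one active sentinel (Protocol Section 5.1.1) and sampling planned to 168 h.

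**Working it through.** The documents state no numerical %AUCex, so there is no figure of the plan's own to reproduce. The check is algebra, followed by an illustration of size.

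**Algebra.** Let A = AUC(0-t) and X = C(t)/λz. Table 7 gives AUC(0-∞) = A + X.

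- As worded: f = X/(A + X).
- As the formula stands: (A + X)/A − 1 = X/A.
- Since X = f(A + X) and A = (1 − f)(A + X), X/A = f/(1 − f).

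The formula inflates the share by the factor 1/(1 − f). This result is exact and needs no assumption about the drug.

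| Share as worded, f | Value from the formula, f/(1 − f) |
|---|---|
| 5% | 5.3% |
| 10% | 11.1% |
| 20% | 25.0% |
| 30% | 42.9% |
| 50% | 100% |
| 60% | 150% |

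**Illustration, one-compartment decline.** Here f = 2^(−t_last/t½). Inputs from the documents are t½ of about 35 h (Protocol Section 9.3) and last planned samples at 72 h for Cohorts 1 and 2 and 168 h for Cohort 3 (Protocol Section 9.5.1). The last quantifiable time is an assumption. No assay limit is given, and Protocol Table 9 predicts a Cmax of only 0.004 and 0.01 µg/mL at 0.1 and 0.25 mg, so earlier times are shown too.

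| t½ | t_last | f as worded | Value from the formula |
|---|---|---|---|
| 35 h | 48 h | 38.7% | 63.0% |
| 35 h | 60 h | 30.5% | 43.8% |
| 35 h | 72 h | 24.0% | 31.6% |
| 35 h | 168 h | 3.6% | 3.7% |
| 25 h (assumed) | 72 h | 13.6% | 15.7% |
| 45 h (assumed) | 72 h | 33.0% | 49.2% |

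For the third row: 2^(−72/35) = 0.240, and 0.240/(1 − 0.240) = 0.316.

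**Illustration, two-phase decline.** An early distribution phase makes the extrapolated share smaller. Take C(t)/C0 = (1 − B)·e^(−αt) + B·e^(−βt), with β = ln 2/35 per hour. Choose B so that AUC(0-24)/C0 = 9.92 h, the value for a single exponential with the predicted 7.8 h half-life: (7.8/ln 2) × (1 − 2^(−24/7.8)) = 9.92. With t_last = 72 h:

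| Early half-life (assumed) | B | f as worded | Value from the formula |
|---|---|---|---|
| 0.5 h | 0.500 | 23.7% | 31.0% |
| 2 h | 0.434 | 22.4% | 28.8% |
| 4 h | 0.316 | 19.3% | 23.9% |
| 6 h | 0.164 | 12.8% | 14.7% |

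The lower end is sensitive to the ratio. Protocol Table 9's rounded Cmax gives 0.036/0.004 = 9.0 h for the 0.1 mg dose. With that ratio the 6 h case falls to 8.1%, given as 8.9%, while the 0.5 h case barely moves (23.6%, given as 30.9%). Replacing the rounded Cmax by dose over the 27 L volume in Protocol Section 5.4.1 gives 0.036/(0.1/27) = 9.7 h and 0.091/(0.25/27) = 9.8 h for the two doses, close to 9.92.

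**The case against.** The strongest objection is that the formula may have been misread from the PDF. Formulas elsewhere in this SAP as read are doubtful: Section 11.6.3 shows QTcB with a fourth root of RR, yet the same section derives RR from the square of QT/QTcB. A well-formed expression is therefore no proof of a correct reading, and the page must be checked. Against that, one simple slip would not turn a correct formula into this one. Swapping only numerator and denominator gives AUC(0-t)/AUC(0-∞) − 1 = −f, a negative number. The form [1 − AUC(0-t)/AUC(0-∞)] × 100 differs in both the fraction and the order of subtraction.

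Second, the formula may never be executed. Parameters come from standard non-compartmental analysis in WinNonlin, and SAP Section 11.5.3 marks "PK Parameter to be Derived by Programmer" as not applicable. This stands, and whether a reported value would be wrong cannot be settled from the documents. If WinNonlin uses the worded definition, the SAP still misdescribes its own output.

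Third, little depends on the number. %AUCex is outside the named summary parameters, so a listing is its most likely appearance. No population or decision uses it, the PK analysis is descriptive, and the PK/PD analysis was dropped. Anyone with AUC(0-t) and AUC(0-∞) can recompute the share. All of this stands and keeps the point minor, but it does not make the row consistent.

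**Conclusion.** The concern holds. As the SAP text reads, the %AUCex row contradicts itself, and following its formula reports f/(1 − f) in place of f. The algebra is exact; confidence is medium because the formula still has to be confirmed on the source page.

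The likely size in Cohorts 1 and 2 is a moderate overstatement: 24.0% given as 31.6% under a one-compartment decline with a 35 h half-life and a quantifiable 72 h sample. It is larger if concentrations become unquantifiable sooner, and smaller if there is a marked distribution phase. In Cohort 3 the gap is negligible if sampling ran to 168 h. AUC(0-∞), CL, Vdss and t½ are unaffected. Severity is minor.

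**What to change.** First check the formula on the source page. If it stands as read, replace it in Table 7 with

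%AUCex = 100 × [AUC(0-∞) − AUC(0-t)] / AUC(0-∞),

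which is the same as [1 − AUC(0-t)/AUC(0-∞)] × 100 and returns exactly the share described in words. Then confirm that any %AUCex listed from the WinNonlin output follows that definition. The cost is one formula and one output check, with no new data or analysis.
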